6.4. Subject Withdrawal

An investigator and/or sponsor can withdraw a subject from the study if deemed appropriate. In addition, if a subject fails to continue to meet the inclusion criteria, new information becomes available that would exclude the subject, or the subject develops a condition or situation that would meet exclusion criteria, the subject may be considered for withdrawal.

Reasons why a subject may discontinue or be withdrawn from the study include, but are not limited to, failure to meet entrance criteria (screening failure), AE, death, pregnancy, protocol deviation, lost to follow-up, no longer willing to participate in the study, study terminated by the sponsor, or any other reason. Subjects who have received the investigational product will not be replaced, regardless of the reason for withdrawal.

The investigator should capture the reason for withdrawal in the database for all subjects and a 6-month postvaccination follow-up telephone contact for the collection of safety information should be completed for all subjects who have been withdrawn after administration of investigational product.

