2.1.2. Primary Endpoints

- Proportions of subjects reporting prompted local reactions within 14 days after vaccination (redness, swelling, and pain at the injection site).
- Proportions of subjects reporting prompted systemic events within 14 days after vaccination (fever, headache, fatigue, muscle pain, and joint pain).
- Proportions of subjects reporting adverse events (AEs) within 1 month after vaccination.
- Proportions of subjects reporting serious adverse events (SAEs) and newly diagnosed chronic medical conditions (NDCMCs) within 6 months after vaccination (both Stage 1 and Stage 2) and within 12 months after vaccination (Stage 2 only).

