10. Subjects who receive treatment with immunosuppressive therapy, including cytotoxic agents or systemic corticosteroids, or planned receipt through the last postvaccination blood draw. If systemic corticosteroids have been administered short term (<14 days) for treatment of an acute illness, subjects should not be enrolled into the study until corticosteroid therapy has been discontinued for at least 28 days before investigational product administration. Inhaled/nebulized, intra-articular, intrabursal, or topical (skin or eyes) corticosteroids are permitted.
11. Subjects with known or suspected immunodeficiency or other conditions associated with immunosuppression, including, but not limited to, immunoglobulin class/subclass deficiencies, generalized malignancy, human immunodeficiency virus (HIV) infection, leukemia, lymphoma, or organ or bone marrow transplant.
12. Bleeding diathesis or condition associated with prolonged bleeding that would, in the opinion of the investigator, contraindicate intramuscular injection.
13. Receipt of blood/plasma products or immunoglobulin, within 60 days before investigational product administration, or planned receipt through study participation.
14. Pregnant female subjects or breastfeeding female subjects (known or suspected).

Stage 2

1. Investigator site staff members directly involved in the conduct of the study and their family members, site staff members otherwise supervised by the investigator, or subjects who are Pfizer employees, including their family members, directly involved in the conduct of the study.
2. Participation in other studies involving investigational drug(s), vaccines, or medical device(s) within 28 prior to study entry and/or during study duration. Participation in purely observational studies is acceptable.

3. Serious chronic disorder including metastatic malignancy, severe chronic obstructive pulmonary disease (COPD) requiring supplemental oxygen, end-stage renal disease with or without dialysis, clinically unstable cardiac disease, or any other disorder that in the investigator's opinion excludes the subject from participating in the study.

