- Ask the subject to contact the site staff or investigator immediately if he or she experiences fever $>104.0^{\circ}\text{F}$ ($>40.0^{\circ}\text{C}$) or Grade 3 local reaction (ie, redness or swelling at the injection site measuring ≥ 21 measuring device units [$\geq 10.5\text{ cm}$], or severe injection site pain [prevents daily activity]) to determine if the event requires further assessment by the investigator.
- Subjects will also be instructed to contact site staff if they experience any possible Grade 4 prompted local reaction or systemic event (refer to [Section 7.2.3](#)).
- Remind the subject that study staff may assess him or her to obtain additional information on Grade 3 events entered into the e-diary.
- Ask the subject to notify the investigator or site staff immediately if any significant illness or medical event (eg, emergency room visit or hospitalization) occurs during the study period.
- Remind the subject to use appropriate contraceptives until 28 days after vaccination, if applicable.
- Record AEs as described in [Section 8](#).
- The investigator or an authorized designee completes the CRF and updates the investigational product accountability records.
- The investigator or appropriately qualified designee reviews the e-diary data online at frequent intervals (daily is optimal) for the 14 days following vaccination to evaluate subject compliance and as part of the ongoing safety review.

6.2.2. Visit 2 (Month 1; 28 to 35 Days After Vaccination) – Clinic Visit

- Ensure and document that the subject continues to be eligible for the study and that none of the temporary blood draw delay criteria are met.
- Perform a contraception check (see [Section 4.4.1](#)), if applicable.

- Record nonstudy vaccinations and concomitant medications as described in [Section 5.11.3](#).
- Collect a blood sample of approximately 50 mL for immunogenicity assessments.
- Review the subject's e-diary data and collect the e-diary. Collect stop dates of any e-diary events ongoing on the last day that the e-diary was completed and record stop dates in the CRF.
- Determine whether any AEs, SAEs, or NDCMCs have occurred since Visit 1 and follow up on any previously reported ongoing AEs, SAEs, or NDCMCs to determine the outcome (ie, record stop dates or confirm if they are still continuing) and record as described in [Section 8](#).

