- Remind the subject to contact the investigator or site staff immediately if any significant illness or medical event (eg, emergency room visit or hospitalization) occurs during the study period.
- The investigator or an authorized designee completes the CRF.

6.2.3. Visit 3 (Month 6; 168 to 196 Days After Vaccination) – Telephone Contact

- Record nonstudy vaccinations and concomitant medications as described in [Section 5.11.3](#).
- Ensure and document that the subject continues to be eligible for the study.
- Determine whether any NDCMCs or SAEs have occurred since Visit 2 and follow up on any previously reported ongoing AEs, SAEs, or NDCMCs to determine the outcome (ie, record stop dates or confirm if they are still continuing) and record as described in [Section 8](#).
- The investigator or an authorized designee completes the CRF.

6.2.4. Visit 4 (Month 12; 350 to 378 Days After Vaccination) – Clinic Visit

- Ensure and document that none of the temporary blood draw delay criteria are met.
- Record nonstudy vaccinations and concomitant medications as described in [Section 5.11.3](#).

- CCI
- Determine whether any SAEs or NDCMCs have occurred since Visit 3 and follow up on any previously reported AEs, SAEs, or NDCMCs to determine the outcome (ie, record stop dates or confirm if they are still continuing) and record as described in [Section 8](#).
- The investigator or an authorized designee completes the CRF.

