6.4.1. Withdrawal of Consent

Subjects who request to discontinue after receipt of investigational product will remain in the study and must continue to be followed for protocol-specified follow-up procedures. The only exception to this is when a subject specifically withdraws consent for any further contact with him or her or persons previously authorized by the subject to provide this information. Subjects should notify the investigator in writing of the decision to withdraw consent from future follow-up, whenever possible. The withdrawal of consent should be explained in detail in the medical records by the investigator and entered on the appropriate CRF page. In the event that vital status (whether the subject is alive or dead) is being measured, publicly available information should be used to determine vital status only as appropriately directed in accordance with local law.

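### Stage 2 subjects can be withdrawn after the only dose for developing a condition that the primary endpoint counts, and no text then carries SAE/NDCMC collection from Month 6 to Month 12

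*Protocol*

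**What the plan says.** - **Dosing.** Every subject gets one injection, at Visit 1 (Protocol 5.7). No later dose is planned.
- **Endpoint.** The primary endpoint at issue (Protocol 2.1.2) is the share of subjects reporting SAEs, taken together with: "newly diagnosed chronic medical conditions (NDCMCs) within 6 months after vaccination (both Stage 1 and Stage 2) and within 12 months after vaccination (Stage 2". The 12-month part applies to that stage alone.
- **Checks after dosing.** At Stage 2 Visit 2 (6.2.2) the site must "Ensure and document that the subject continues to be eligible for the study and that none of the temporary blood draw delay criteria are met". At the Stage 2 Month 6 call (6.2.3) it must again "Ensure and document that the subject continues to be eligible for the study". Stage 1 has the check at Visit 2 (6.1.3) but not at its Month 6 call.
- **Withdrawal trigger.** Section 6.4 says that if "the subject develops a condition or situation that would meet exclusion criteria, the subject may be considered for withdrawal". Its list of reasons for leaving the study includes "failure to meet entrance criteria (screening failure), AE, death, pregnancy, protocol deviation, lost to follow-up".
- **Overlap.** Stage 2 exclusion 3 begins "Serious chronic disorder including metastatic malignancy, severe chronic obstructive pulmonary disease (COPD) requiring supplemental oxygen" and goes on to end-stage renal disease and unstable cardiac disease. Exclusions 7 and 9 cover proven invasive pneumococcal disease, immunodeficiency, leukemia and lymphoma (4.2).
- **Contact after withdrawal.** Section 6.4 also states that "a 6-month postvaccination follow-up telephone contact for the collection of safety information should be completed for all subjects who have been withdrawn" after dosing. It names no later contact.
- **Subjects who ask to stop.** Section 6.4.1: "Subjects who request to discontinue after receipt of investigational product will remain in the study and must continue to be followed".
- **Analysis.** SAP 8.2.1.3 summarizes SAEs and NDCMCs cumulatively to 12 months (item 3) and separately from the 6-month follow-up to 12 months (item 5).

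**The concern.** Once the only dose has been given, an eligibility check cannot prevent further exposure to study vaccine. Yet it feeds a rule under which a new serious illness can take the subject out of the study, and that illness may be the very event the primary endpoint counts. Loss of follow-up then depends on the outcome, and the subjects removed are plausibly those at higher risk of further events.

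The protocol is also uneven. A subject who asks to stop is kept in follow-up (6.4.1), and one who becomes pregnant after dosing may remain for safety monitoring (7.1). A subject withdrawn by the investigator or sponsor for a new illness has no stated follow-up after the 6-month call. The Stage 2 Month 6 check sits just before that unprotected period.

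The SAP does not repair this. Section 7 gives missing-value rules for immunogenicity and e-diary data but none for AEs, SAEs or NDCMCs. Section 5.1 permits subjects with no safety data for an analysis to be left out of it. How a subject withdrawn at Month 6 enters the Month 6 to 12 summary is therefore not stated.

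**Working it through.** The plan gives no figure on this point, so there is none to reproduce. The check has three steps.

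**1. Follow-up that the text does not protect**

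Inputs: the Stage 2 Month 6 contact is at 168 to 196 days (6.2.3) and the Month 12 visit at 350 to 378 days (6.2.4). Matching the ends of the windows:

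- 350 − 168 = 182 days, and 182/350 = 52%
- 378 − 196 = 182 days, and 182/378 = 48%

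So about half of the 12-month window has no planned contact for a withdrawn subject. In Stage 1, SAE/NDCMC follow-up ends at Month 6, so nothing is lost by rule if the call is made.

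**2. What the loss can change**

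| Quantity | Effect of losing Months 6 to 12 |
|---|---|
| Event that triggered withdrawal | None. An SAE leading to withdrawal must be recorded (Protocol 8.1.3) |
| Cumulative proportion with any SAE, trigger was an SAE | None. The subject already counts |
| Cumulative proportion with any SAE, trigger was a nonserious NDCMC | A later SAE can be missed |
| Proportion for a given preferred term | A later event under another term can be missed |
| Month 6 to 12 interval summary (SAP 8.2.1.3, item 5) | Any later event can be missed |

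**3. Size**

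The arm size is 440/2 = 220 (Protocol 3.3). The other inputs are not in the documents and are assumed:

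- q, share with a triggering SAE or NDCMC by Month 6: 2% to 10%
- w, share of those who are withdrawn: 25% to 100%
- s, chance of a further countable event in Months 6 to 12: 5% to 40%

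Subjects missed per arm = 220 × q × w × s. Percentage points = 100 × q × w × s.

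| Case | q | w | s | Subjects per arm | Points |
|---|---|---|---|---|---|
| Low | 2% | 25% | 5% | 0.06 | 0.03 |
| Middle | 5% | 50% | 20% | 1.1 | 0.5 |
| High | 10% | 100% | 40% | 8.8 | 4.0 |

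For scale, the Clopper-Pearson 95% interval for 7 of 220 runs from 1.3% to 6.4%. The middle case is small beside that width; the high case is not.

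**The case against.** The strongest reply is that the protocol already limits the damage.

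- **The 6-month call.** It covers every subject withdrawn after dosing. This stands, and it confines the point to Stage 2, Months 6 to 12. The Month 6 check also takes place in the same call that collects SAEs and NDCMCs, so data up to that date are captured.
- **Withdrawal is optional.** Section 6.4 allows it and does not require it. This stands, and is why w starts at 25% above. But the section gives no criteria, so practice can differ between sites.
- **Other safeguards.** Section 6.4.2 asks for every effort to document outcome, a final visit if applicable, and follow-up of unresolved AEs. Section 8.1.4.1 has later SAEs reported when the investigator learns of them. These help with known events. They do not schedule an enquiry about new SAEs or NDCMCs up to Month 12.
- **The check may have another use.** Nonstudy pneumococcal vaccines are prohibited throughout participation (5.11.1), and a later Stage 2 immunogenicity population may lie behind the redactions. This is fair, and the Month 6 check should not be called pointless. Those uses need a record of deviations, not a withdrawal.
- **Section 6.4.1 covers a different trigger.** It deals with subject requests, so it does not contradict 6.4. It does show that follow-up after discontinuation is thought both feasible and desirable.

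A reader might also infer that the Visit 2 check, listed before the blood draw, costs the Month 1 OPA sample. Neither 6.1.3 nor 6.2.2 says to skip the draw if eligibility has lapsed, so that is only a possibility.

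**Conclusion.** The point holds for Stage 2, Months 6 to 12. The text permits withdrawal because of a condition that may be an SAE or NDCMC, and it secures no SAE/NDCMC collection after the 6-month call. The exposed part is about half of the 12-month primary window. The size is unknown: 0.03 to 4.0 percentage points per arm under the assumed rates, 0.5 in the middle case. The study is descriptive, so no test or power claim is affected.

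Two stronger readings are tempting and are not supported.

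- **That safety follow-up in general stops because of the outcome, in both stages.** The 6-month call and the recording of the triggering SAE rule this out for follow-up to Month 6, which is all of Stage 1.
- **That the 12-month SAE proportion is 7% to 30% too low.** Such figures arise by assuming that 1%, 3% or 5% of 220 subjects (2.2, 6.6 or 11) are all withdrawn, with a Month 6 to 12 SAE risk of 20% against 2.5% in the rest. The expected count then falls from 5.89 to 5.45, 6.66 to 5.34, or 7.43 to 5.23. That takes an optional withdrawal as certain, rests on risks found in neither document, and describes the interval table, not the cumulative proportion of subjects. In absolute terms the drop is 0.44, 1.32 or 2.2 subjects, or 0.2, 0.6 or 1.0 points.

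This is a cheap improvement to secure a primary endpoint, not evidence that the endpoint is invalid.

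**What to change.** 1. **Protocol 6.4.** State that a condition arising, or eligibility information emerging, after vaccination does not by itself end safety follow-up. Subject to consent and the investigator's safety judgment, such Stage 2 subjects stay in scheduled SAE/NDCMC collection to Month 12, in line with 6.4.1.
2. **Protocol 6.2.2, 6.2.3 and the Stage 2 schedule.** Say that the eligibility checks at Visit 2 and Month 6 serve only to document deviations and to classify subjects for the evaluable immunogenicity populations (Protocol 9.2, SAP 5.2.1.1).

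Cost: an amendment to wording and a few more subjects to follow to Month 12. No new procedures are needed.

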6.4.1. Withdrawal of Consent

Subjects who request to discontinue after receipt of investigational product will remain in the study and must continue to be followed for protocol-specified follow-up procedures. The only exception to this is when a subject specifically withdraws consent for any further contact with him or her or persons previously authorized by the subject to provide this information. Subjects should notify the investigator in writing of the decision to withdraw consent from future follow-up, whenever possible. The withdrawal of consent should be explained in detail in the medical records by the investigator and entered on the appropriate CRF page. In the event that vital status (whether the subject is alive or dead) is being measured, publicly available information should be used to determine vital status only as appropriately directed in accordance with local law.

6.4.2. Lost to Follow-up

All reasonable efforts must be made to locate subjects to determine and report their ongoing status. This includes follow-up with persons authorized by the subject as noted above. Lost to follow-up is defined by the inability to reach the subject after a minimum of 2 documented phone calls, faxes, or emails as well as lack of response by the subject to 1 registered mail letter. All attempts should be documented in the subject's medical records. If it is determined that the subject has died, the site will use locally permissible methods to obtain the date and cause of death. If the investigator's use of a third-party representative to assist in the follow-up portion of the study has been included in the subject's informed consent, then the investigator may use a sponsor-retained third-party representative to assist site staff with obtaining the subject's contact information or other public vital status data necessary to complete the follow-up portion of the study. The site staff and representative will consult

publicly available sources, such as public health registries and databases, in order to obtain updated contact information. If, after all attempts, the subject remains lost to follow-up, then the last-known-alive date as determined by the investigator should be reported and documented in the subject's medical records.

Subjects may withdraw from the study at any time at their own request, or they may be withdrawn at any time at the discretion of the investigator or sponsor for safety (see also Withdrawal From the Study Due to Adverse Events, [Section 8.1.3](#)) or behavioral reasons, or the inability of the subject to comply with the protocol-required schedule of study visits or procedures at a given study site.

If a subject does not return for a scheduled visit, every effort should be made to contact the subject. All attempts to contact the subject and information received during contact attempts must be documented in the subject's medical record. In any circumstance, every effort should be made to document subject outcome, if possible. The investigator should inquire about the reason for withdrawal, request that the subject return for a final visit, if applicable, and follow up with the subject regarding any unresolved AEs.

If the subject withdraws from the study, and also withdraws consent for disclosure of future information, no further evaluations should be performed, and no additional data should be collected. The sponsor may retain and continue to use any data collected before such withdrawal of consent.

7. ASSESSMENTS

Every effort should be made to ensure that the protocol-required tests and procedures are completed as described. However, it is anticipated that from time to time there may be circumstances outside of the control of the investigator that may make it unfeasible to perform the test. In these cases the investigator will take all steps necessary to ensure the safety and well-being of the subject. When a protocol-required test cannot be performed, the investigator will document the reason for this and any corrective and preventive actions that he or she has taken to ensure that normal processes are adhered to as soon as possible. The study team will be informed of these incidents in a timely manner.

For samples being collected and shipped, detailed collection, processing, storage, and shipment instructions and contact information will be provided to the investigator site prior to initiation of the study.

7.1. Pregnancy Testing

For female subjects of childbearing potential, a urine pregnancy test, with sensitivity of at least 25 mIU/mL, will be performed immediately before administration of the investigational product. A negative pregnancy test result is required before the subject may receive the investigational product. Pregnancy tests may also be repeated if requested by institutional review boards (IRBs)/ethics committees (ECs) or if required by local regulations. In the case of a positive confirmed pregnancy at Visit 1, the subject will be withdrawn from administration of investigational product and from the study. In the case of a positive

confirmed pregnancy after administration of investigational product, the subject may remain in the study for safety monitoring.

7.2. Safety Parameters

Safety parameters will be assessed as described in the [Schedule of Activities, Section 6](#), and below.

A medical history, physical examination, and measurement of oral temperature will be performed on all subjects prior to vaccination to determine subject eligibility and to establish a clinical baseline. Significant medical history and observations from the physical examination and temperature measurement will be documented and recorded in the CRF.

Acute reactions within the first 30 minutes after investigational product administration will be assessed and documented as an AE or SAE, as appropriate, in the CRF.

Prompted e-diary events, including local reactions and systemic events that occur in the 14 days after investigational product administration at Visit 1, are graded as described in [Section 7.2.3](#). In addition, safety laboratory testing as described in [Section 7.4](#) will be performed in Stage 1. Furthermore, AEs, SAEs, and NDCMCs will be collected as defined in [Section 8](#).

CCI

CCI

